2.4.8 Sample Size

The sample size calculation was performed for detecting a significant difference between correlations on % pain reduction vs. MPT slopes of pregabalin and placebo in linear bivariate regression. Assuming slope and SD data based on our preliminary results of MPT vs. response with another drug, lidocaine (Haroutiunian, Nikolajsen et al. 2013); to detect 0.3 (SD=0.5) difference in correlation coefficients between the two slopes, with 85% power and alpha=0.05, 27 participant are required in this cross-over design. We will aim to recruit 35 patients to account for possible 20% dropout rate.

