2.4.4 Minimization of Bias

There will be no specific sex, ethnic or racial background for enrollment. Placebo arm is introduced to increase the ability to differentiate between the pharmacologic effects of pregabalin and

other possible effects. The study is designed as a cross-over in order to minimize inter-subject variability. The investigators and the subjects will be blinded to treatment allocation sequence.

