2.4.7 Statistical Methods

The primary outcome is the comparison of slopes of the two correlations: baseline MPT vs % pain reduction with pregabalin, and baseline MPT vs % pain reduction with placebo. Percent pain reduction will be assessed from the difference in average pain intensity at baseline and the average daily pain intensity on days 24-28 of each treatment phase, obtained from the patient diaries. The two slopes will be compared using t-test. Significant difference between slopes will indicate that baseline MPT correlates with pregabalin response (vs. placebo response) in painful CIPN, regardless of differences in average pain response between pregabalin and placebo.

As secondary analyses, we will compare mean absolute pain reduction with pregabalin to absolute pain reduction to placebo (both for average daily pain and maximum daily pain), using paired t-test, given normal data distribution. If normal distribution is not obtained, we will use Wilcoxon signed ranked test. In addition, we will perform Fisher exact test to compare the proportion of patients with 50% or more reduction in average pain intensity from baseline with pregabalin vs. placebo. Number needed to treat (NNT) will be calculated from this proportion of responders to pregabalin and placebo. These secondary analyses are aimed at detecting group differences in response to pregabalin vs. placebo.

In exploratory analysis, we will examine the correlations between the various demographical and QST variables (WDT, CDT, HPT, CPT, WSI, TS, CPM) and pain reduction with pregabalin vs placebo, for generating hypotheses for additional predictors of response to pregabalin in CIPN. We will also perform exploratory multiple regression analysis to evaluate how various QST factors perform in combination as treatment response predictors.

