2.4.9. Dealing with missing data

If less than 10% data on primary outcomes are missing, we will perform our primary analysis per protocol, and perform sensitivity analysis using intent to treat (ITT) approach, where missing pain intensity data will be imputed using last observation carried forward (LOCF) method. If more than 10% primary outcomes data are missing, we will use mixed-effects model imputation method [full information maximum likelihood (Little, D'Agostino et al. 2012)], which considers the reasons for missingness, and is more appropriate for reducing bias.

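### The 85% power with 27 patients is not established for the primary slope comparison: section 2.4.8 mixes slopes with correlations and leaves the SD of 0.5 undefined, and section 2.4.7 does not say the slope test is paired

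*Combined protocol and SAP*

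**What the plan says.** Section 2.4.8 (Sample Size) describes the target as a "significant difference between correlations on % pain reduction vs. MPT slopes of pregabalin and placebo in linear bivariate regression". It takes its inputs from elsewhere, "Assuming slope and SD data based on our preliminary results of MPT vs. response with another drug, lidocaine", and then says that "to detect 0.3 (SD=0.5) difference in correlation coefficients between the two slopes, with 85% power and alpha=0.05, 27 participant are required" in the cross-over. The section does not give the SD of MPT, a residual SD, the two correlations, the correlation between a patient's two responses, or whether alpha is one- or two-sided.

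Section 2.4.7 (Statistical Methods) says of the primary analysis: "The two slopes will be compared using t-test". The next paragraph of that section compares mean absolute pain reduction between treatments "using paired t-test, given normal data distribution". Section 2.4.4 gives the reason for the design: "The study is designed as a cross-over in order to minimize inter-subject variability". Section 2.4.9 mentions a mixed-effects approach, but only for incomplete data: "If more than 10% primary outcomes data are missing, we will use mixed-effects model imputation method".

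On numbers, section 2.4.8 says "We will aim to recruit 35 patients to account for possible 20% dropout rate", whereas the Synopsis and sections 2.3 and 2.4.1 speak of 35 evaluable patients.

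**The concern.** A correlation is one number per treatment. A difference between two correlations therefore has no per-patient SD, and attaching an SD of 0.5 to it leaves the effect without a clear meaning. Power for a slope difference needs the spread of MPT and the residual SD. Power for a difference between two correlations measured in the same patients needs rho, the correlation of their responses on the two treatments. The plan supplies none of these, so the reader cannot tell which quantity has 85% power.

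A related gap is the form of the test. Both slopes come from the same patients, so their estimates are correlated. The ordinary t-test for two slopes treats them as independent. Because the plan writes paired for the secondary comparison and not for the primary one, two analysts could run different primary tests. One of them would give up the gain for which the cross-over was chosen.

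This is the trial's only primary test and its only power statement.

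**Working it through.** **Inputs from section 2.4.8:** difference 0.3, SD 0.5, alpha 0.05, power 85%, n = 27. **Assumptions, not in the documents:** two-sided test, the scale of MPT, rho, and equal outcome variances in step 4. All power figures use the noncentral t distribution, except those in step 5, which are simulated.

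**1. Reproducing the plan's figure.** For a paired t-test on a mean difference, the noncentrality is (0.3/0.5) × √n with n − 1 degrees of freedom. At n = 27 this is 0.6 × 5.196 = 3.118 on 26 df, giving 85.1%. At n = 26 the power is 83.6%. So 27 is exactly the smallest n that reaches 85%.

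**2. The same inputs as a paired slope test.** Regress the within-patient difference in response on MPT. The noncentrality is 0.3 × SD(MPT) × √n / 0.5 with n − 2 df.
- With SD(MPT) = 1 (0.3 is per SD of MPT) and 0.5 the residual SD of the difference, the noncentrality is again 3.118, now on 25 df: 85.0% with MPT values fixed, 81.1% when averaged over sampled MPT values.
- Steps 1 and 2 differ by about 0.1 point with MPT fixed, so the figures cannot show which calculation was done.
- With 0.3 per unit of another MPT scale (MPT fixed), SD(MPT) = 0.5 gives 32% and SD(MPT) = 1.4 gives 99%.

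**3. If 0.5 is the residual SD within each treatment** (SD(MPT) = 1), the residual SD of the difference is 0.5 × √(2(1 − r)), where r is the residual correlation. The range is sampled to fixed MPT.

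| r | SD of difference | Power, n = 27 |
|---|---|---|
| 0 | 0.707 | 54–56% |
| 0.3 | 0.592 | 68–72% |
| 0.5 | 0.500 | 81–85% |

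**4. Read literally as a correlation difference of 0.3.** With unit outcome variances, the residual SD of the within-patient difference is √(2(1 − rho) − 0.3²). Paired test, sampled MPT:

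| rho | Residual SD | Power, n = 27 | n = 28 | n = 35 |
|---|---|---|---|---|
| 0 | 1.382 | 19% | 19% | 23% |
| 0.3 | 1.145 | 25% | 26% | 32% |
| 0.5 | 0.954 | 34% | 35% | 43% |
| 0.7 | 0.714 | 53% | 55% | 65% |
| 0.8 | 0.557 | 73% | 75% | 84% |

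Power of 85% needs rho of about 0.84 at n = 27 or 28, and about 0.80 at n = 35.

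**5. Effect of ignoring the pairing.** Simulation at n = 27 with correlations 0.3 and 0 and assumed rho 0.5: the ordinary two-slope t-test has about 11% power, against about 34% for the paired test. With both correlations 0 and rho 0.5, it rejects less than 1% of the time instead of 5%, so it is too conservative. At rho = 0 there is no loss: both tests have about 19% power.

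**6. Patient count.** 27/0.8 = 33.75, so 34 would do and 35 covers it. 35 × 0.8 = 28 evaluable. The dropout arithmetic is sound; only the evaluable wording elsewhere conflicts with it.

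**The case against.** The strongest reply is that the calculation may be right as it stands. Section 2.4.8 refers to slope and SD data and to bivariate regression, which points to a slope calculation, and step 2 shows that a natural scaling returns 85.0% at 27. That stands. A reader might infer from the match with a paired mean-difference test that the wrong formula was used. The documents do not support that, because the two calculations give almost the same answer. No arithmetic error is shown.

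A reader might also infer that the trial is underpowered. That is not shown either. The low figures in step 4 depend on an assumed rho and on equal variances, and step 2 shows that other scalings give power at or above the stated figure. The cited lidocaine data may define the scale, but the plan does not reproduce them.

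Nor does the plan prescribe an unpaired test. Section 2.4.8 relies on the cross-over and section 2.4.4 explains why it was chosen, so pairing may well be intended. The figures in step 5 illustrate what the omission could cost; they do not describe the planned analysis.

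Finally, section 2.4.1 calls this a pilot, and a null finding could still be read from the estimated slope difference and its confidence interval. It would go too far to say that such a result could not be interpreted. The plan nevertheless states a hypothesis test with 85% power, and that statement should be traceable to the test.

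**Conclusion.** The point holds as a gap in specification: 85% is not demonstrated for the primary slope comparison, and it is not shown to be wrong. At n = 27, under a two-sided test, power is 81–85% on the favourable slope reading. On the literal correlation reading it is about 19, 34, 53 and 73% at assumed rho 0, 0.5, 0.7 and 0.8. Other MPT scalings move it from 32% to 99%. The documents do not settle which of these applies. The missing word on pairing is a smaller gap. It matters only if responses are positively correlated within patients, in which case the ordinary test is conservative and loses power.

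The evaluable count is a separate wording matter and adds no weight to this conclusion.

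**What to change.** - **Section 2.4.7:** state that the primary test is paired. Either regress the within-patient difference in percentage pain reduction on baseline MPT, or use the treatment-by-MPT term of a mixed model with a patient effect.
- **Section 2.4.8:** use one scale, slope or correlation. Define 0.3 and 0.5 on it, give the SD of MPT and the sidedness, and recompute the power for the model named in 2.4.7.
- **If the source data do not support 85%:** restate the power, or give the detectable difference over a range of rho, with N unchanged. On the correlation scale with equal variances, the difference detectable with 80–85% power is 0.50–0.53 at rho 0.5 and 0.32–0.33 at rho 0.8 for 28 evaluable patients. For 35 evaluable it is 0.45–0.48 and 0.29–0.30.
- **Separately:** reconcile 35 evaluable (Synopsis, 2.3, 2.4.1) with 35 recruited allowing for 20% dropout, about 28 evaluable (2.4.8).

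The cost is protocol wording and one recalculation, with no extra patients or visits. The downside is that the stated power may become less favourable.

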2.4.9. Dealing with missing data

If less than 10% data on primary outcomes are missing, we will perform our primary analysis per protocol, and perform sensitivity analysis using intent to treat (ITT) approach, where missing pain intensity data will be imputed using last observation carried forward (LOCF) method. If more than 10% primary outcomes data are missing, we will use mixed-effects model imputation method [full information maximum likelihood (Little, D'Agostino et al. 2012)], which considers the reasons for missingness, and is more appropriate for reducing bias.

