Patients will complete an electronic diary with daily report of their average and maximum daily pain intensity, recorded every evening before bedtime. The percentage of pain reduction for primary outcome will be assessed from the difference between baseline average pain intensity and the average pain intensity of last 5 days of treatment (day 24-28), on 0-10 NRS.

Secondary efficacy outcomes will include: 1) The difference between baseline maximum pain intensity and the maximum pain intensity of the last 5 days of treatment, on 0-10 NRS; 2) The proportion of patients achieving 50% or more pain relief with pregabalin vs. placebo treatment; 3) Difference in Pain Severity and Pain Interference scales of the BPI, assessed at baseline and day 28 of treatment. The daily use of rescue analgesia (oral acetaminophen) will also be recorded.

Table 1. Data assessment schedule

Required Assessments	Screening and Enrollment Baseline Visit	Week 1a	Week 2a	Week 3a	Week 4a	End of Treatment A (Day 28 +/- 2)	Wash-out	Study crossover visit	Week 1b	Week 2b	Week 3b	Week 4b	End of Study Visit (Day 30 +/- 3)
Study visits	Visit1 (a/b)*					Visit2		Visit3					Visit 4
Informed consent	✓												
Pregnancy (urine Hbhcg) test for women	✓												
Comprehensive Metabolic Panel (CMP) blood test**	✓					✓							✓
Inclusion/exclusion criteria	✓												
Randomization	✓												
Demographic data collection	✓												
Sensory Mapping	✓					✓		✓					✓
BPI questionnaire	✓				✓			✓				✓	
NPSI questionnaire	✓				✓			✓				✓	
DAPOS questionnaire	✓				✓			✓				✓	
SPI questionnaire	✓				✓			✓				✓	
QST	✓							✓					
CPM	✓							✓					
Dispense study drug	✓							✓					
Pain intensity 0-10 NRS	✓	daily	daily	daily	daily			✓	daily	daily	daily	daily	✓
Adverse Event assessment		daily	daily	daily	daily				daily	daily	daily	daily	✓
Telephone communication		weekly	weekly	weekly	weekly				weekly	weekly	weekly	weekly	
Blinding questionnaire***		✓											
Pill count								✓					✓
Blood sample (PK)						✓							✓
Skin biopsy (optional)													✓

*Visit 1 may be conducted over 2 visits to complete all assessments if required for subject tolerability or convenience

** A blood sample for CMP will not be obtained if recent (<30 days) results are available.

*** Blinding questionnaire to be administered via EMA device on Day 5 of study drug treatment

Subject Blinding Perception

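### Section 2.4.9 lets the observed amount of missing data choose the primary analysis, with no unit for the 10% threshold and no rule at exactly 10%; one pre-specified mixed model would remove the switch

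*Combined protocol and SAP*

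**What the plan says.** Section 2.4.9 (Dealing with missing data) sets two branches.

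- Below the threshold: "If less than 10% data on primary outcomes are missing, we will perform our primary analysis per protocol". An intention-to-treat analysis is then a sensitivity analysis only, in which "missing pain intensity data will be imputed using last observation carried forward (LOCF) method".
- Above it: "If more than 10% primary outcomes data are missing, we will use mixed-effects model imputation method". The section describes this method as one "which considers the reasons for missingness, and is more appropriate for reducing bias".

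The section does not say what is counted, what happens at exactly 10%, who is in the per-protocol set, or who is in the likelihood analysis.

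The primary outcome itself is set out elsewhere. Section 2.4.7 takes percent pain reduction from baseline and "the average daily pain intensity on days 24-28 of each treatment phase", and says of the primary test: "The two slopes will be compared using t-test". Section 2.4.3 (Clinical Efficacy) gives the same five-day window, "the average pain intensity of last 5 days of treatment (day 24-28", from a diary "recorded every evening before bedtime".

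Section 2.4.8 plans for 20% dropout. Section 3.2 withdraws patients for grade 3 or higher adverse effects and for needing more of their other analgesics. It also lets a patient who stops during the first phase go on to the second.

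**The concern.** The primary analysis is not known until the missing data have been counted, and the plan does not say how to count them. Two analysts holding the same data could run different primary analyses and both be following the plan.

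The branches also differ in whom they analyse. Under Section 3.2, randomised patients can be withdrawn for reasons related to treatment, and a per-protocol analysis can leave them out. Below the threshold, the full randomised group appears only in an LOCF sensitivity analysis, although the plan itself regards the likelihood method as the better protection against bias. Patients with one usable period are foreseeable, yet Section 2.4.7 does not say whether they enter the slope comparison.

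The description of the likelihood method also goes too far. Withdrawal reasons are recorded (Section 2.4.3, Safety), but nothing puts them into the model. As named, the method assumes that data are missing at random.

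**Working it through.** **The plan's own figure.** Inputs from Section 2.4.8: difference 0.3, SD 0.5, alpha 0.05 (taken as two-sided), power 85%. For a paired comparison the normal approximation is ((1.960 + 1.036) × 0.5/0.3)² = 24.94, so 25. The exact noncentral t gives 83.7% power at n = 26 and 85.1% at n = 27, which reproduces the stated 27. Allowing for 20% dropout, 27/0.8 = 33.75, or 34; the plan recruits 35. So the sample size is built on pairs, and 35 × 0.2 = 7 dropouts are expected.

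**Applying the 10% rule.** There are 35 patients and 35 × 2 = 70 patient-periods. Let k patients each lack one period.

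| k | k/35 | k/70 | Branch by patient / by period |
|---|---|---|---|
| 3 | 8.6% | 4.3% | per protocol / per protocol |
| 4 | 11.4% | 5.7% | likelihood / per protocol |
| 5 | 14.3% | 7.1% | likelihood / per protocol |
| 6 | 17.1% | 8.6% | likelihood / per protocol |
| 7 | 20.0% | 10.0% | likelihood / no rule |
| 8 | 22.9% | 11.4% | likelihood / likelihood |

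**How often this would occur.** Let each patient drop out with probability p, and let a share s of dropouts lose both periods. The documents do not give s. Each patient then loses 0, 1 or 2 periods with probability 1 − p, p(1 − s) or ps, and these are summed over 35 independent patients. The branches conflict when at least 4 patients but at most 6 periods are affected.

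| s | Conflict, p = 0.20 | Exactly 7/70, p = 0.20 | Conflict, p = 0.10 |
|---|---|---|---|
| 0 | 37.2% | 16.6% | 41.4% |
| 0.25 | 18.9% | 11.7% | 29.0% |
| 0.50 | 8.4% | 7.7% | 16.4% |
| 0.75 | 2.4% | 4.7% | 5.4% |
| 1 | 0% | 0% | 0% |

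The denominator is itself uncertain, because the synopsis and Sections 2.3 and 2.4.1 call for 35 evaluable patients. With 35/0.8 = 43.75, or 44, recruited, the conflict at p = 0.20 is 43/21/9/2/0% over the same values of s.

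**What the choice does to the estimate.** The following is illustrative simulation under assumed inputs: true slope difference −0.300, residual variance 0.91, within-patient correlation 0.3-0.7, and 3 or 6 of 35 patients losing one period. The table gives the attenuation of the slope difference.

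| Who loses what | Complete pairs | Mixed model |
|---|---|---|
| A. Lowest period-1 responders lose period 2 | 3-12% | 0% |
| B. Lowest period-1 responders lose period 1, keep period 2 | 3-12% | 6-15% |
| C. Lowest pregabalin responders lose the pregabalin period | 7-25% | 13-34% |

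Scenario A is missing at random, because the value that drives the loss is observed. In B and C the poor response itself is lost. At n = 35 the mixed model's SD is 0.14-0.22, and its root mean squared error is 0.98-1.03 times that of complete pairs.

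**Calibration of a replacement model.** With 35 patients and no true slope difference, maximum likelihood with a 1.96 cut-off rejected in 6.5-7.9% of simulated trials. REML with a small-sample t reference rejected in 4.4-5.4%, and the complete-pair t-test in 4.6-5.7%.

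**The case against.** The strongest reply is that the rule is pre-specified, in a trial that Section 2.4.1 calls a pilot, and that its trigger is the amount of missing data and not the treatment effect. That is right. A reader might infer that the switch inflates type I error or lets the sponsor pick a favourable result; the documents do not support that inference.

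A second reply is that a mixed model buys no accuracy. This also stands: root mean squared error is about the same, and where the poor response itself is lost the mixed model does worse than complete pairs. Nor would any mixed model do, since an ML fit with a normal cut-off is less well calibrated than the t-test already planned.

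Third, the size of the conflict depends on an unstated split, so 37% is the top of a range at the planned dropout and not an expectation.

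Fourth, two further readings would enlarge the point but are weaker.

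- Counting diary evenings (35 × 2 × 5 = 350) would put the threshold at one missed evening per patient. The LOCF clause on pain scores lends this some support, but the primary outcome is one percentage per phase, so the evening count is the less natural unit.
- Fitting a separate slope per treatment to whatever data exist would give larger biases, but the sample size reproduces only as a paired calculation, so complete pairs is the better-supported reading of the t-test.

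Finally, the simulated biases are not tied to the plan's SD, which would give a standard error of 0.5/√35 = 0.085. They show direction and rough scale only.

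None of this supplies the missing unit, the rule at 10%, or the definition of the per-protocol set. Reading the rule as patient-periods still leaves 7/70 without a branch.

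**Conclusion.** The concern holds and should be acted on. Section 2.4.9 makes the primary analysis depend on a count it does not define, and the ambiguity lies near the plan's own dropout figure. Four to six one-period patients out of 35 select opposite analyses by the two natural counts, and seven fall in no branch when periods are counted. The probability of conflict at 20% dropout runs from 37% to 0% with the share of dropouts who lose both periods. This assumes 35 randomised and independent dropout.

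The case for a single model is that the primary analysis is then fixed beforehand, one-period patients are kept, and the estimate is unbiased if data are missing at random. It does not rest on better accuracy. Nor do the documents show that per-protocol bias would be serious: that depends on who is lost, and in scenarios B and C the likelihood model is attenuated more.

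**What to change.** Delete the 10% switch and pre-specify, whatever the missing fraction:

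- **Primary model.** One mixed model of percent pain reduction with treatment, period, baseline MPT, treatment × MPT and a random patient effect, fitted by REML with Kenward-Roger degrees of freedom. The treatment × MPT term is the slope comparison of Section 2.4.7.
- **Analysis set.** All randomised patients with baseline MPT and a days 24-28 value in at least one period, analysed as randomised. A period value requires at least 3 of the 5 diary evenings; this minimum is a judgement, but it must be fixed.
- **Assumption.** Replace the statement about reasons for missingness with one that the model assumes data are missing at random.
- **Sensitivity analyses.** (a) A complete-pair analysis in a defined per-protocol set. (b) In place of LOCF, a delta-adjusted analysis in all randomised patients, with the range of deltas fixed before unblinding and the recorded withdrawal reasons used.

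The cost is SAP wording and minor programming, with no extra patients or visits. The downside is reliance on missing at random: if the poor response itself is lost, the mixed model is attenuated by about 6-34% against 3-25% for complete pairs in the assumed scenarios, which is why (a) and (b) are needed. Patients with no days 24-28 value in either period are covered only by (b).

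Minimum alternative if the switch is kept: state that the 10% is counted in patient-periods of all randomised patients, and make the upper branch apply at 10% or more.
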